9.1.5 Subject Follow-Up

Make every attempt to follow the subject until the adverse event is resolved, stabilized, returned to baseline or deemed irreversible.

9.2 Special Situations

The Investigator must report all special situations **within 24 hours** by telephone or by fax using the Special Situation form supplied by the Sponsor, to both the Drug Safety group and the Clinical Manager of the Sponsor as listed in Table D.

Special situations include but are not limited to the following: accidental overdose of IP/IMP and/or NIMP, medication error with IP/IMP and/or NIMP (such as administration of the wrong drug or wrong dose, wrong administration rate or wrong technique in drug usage process, administration via the wrong route, radiation under-dose, labeled drug-drug or drug-disease or drug-food interaction). In addition, any notification of lactation or pregnancy of a subject or partner must be reported by the Investigator to the Sponsor within 24 hours using the appropriate

(i.e., Lactation or Pregnancy Report) form. Any associated SAEs must be reported concurrently using the SAER.

In case urgent safety measures are taken during the conduct of the study, these will be communicated in a timely fashion by the Sponsor to the applicable regulatory authorities, IRBs/ECs/REBs and also to concerned investigators and subjects.

9.3 Laboratory Evaluations

9.3.1 Reporting and Evaluation of Central Laboratory Test Results

The central laboratory will send a report of the laboratory results to the Investigator within 48 hours after the sample is picked up from the investigational site. Attach a copy of the laboratory report to the Case Report Form.

The Investigator or sub-investigator must review laboratory values within 24 hours of receipt of the laboratory report. After the review is completed, the Investigator must sign and date each laboratory report.

The central laboratory will provide normal reference ranges for the laboratory tests on the laboratory results report. A value is **normal** when it falls on or within the upper and lower limits of the reference range. A value is **abnormal** when it falls outside the upper or lower limit of the reference range. The central laboratory will flag all abnormal values on the laboratory report and will verify that the result is not due to pre-analytical problems (e.g., sample taken improperly, sample stored incorrectly, sample labeled incorrectly) or to analytical problems (e.g., machine not accurately calibrated, technical problems with equipment or reagents, deterioration of analyte).

The central laboratory has established ‘alert criteria’ for some laboratory tests and will make an **immediate telephone call** to the Investigator in the event that a laboratory result meets these criteria.

The Investigator must evaluate any change from predose to postdose in a laboratory test which represents a worsening of the subject’s clinical state as to whether it meets the definition of an adverse event. **Record all changes determined to meet the definition of an adverse event in the Adverse Event section of the Case Report Form.**

9.3.2 Repeat Testing

Collect additional samples to repeat the lab test that represents a worsening of the subject’s clinical state and meets the definition of an adverse event, until the value returns to the predose level or clinically stabilizes, or until the Investigator or physician of record determines that further follow-up is unnecessary.

9.3.3 Emergency Laboratory Analysis

If a laboratory result needs to be obtained immediately, split the sample and send one-half to the local laboratory for immediate analysis and the other half to the central laboratory. Attach results from both laboratories to the Case Report Form.

9.4 Electrocardiograms

If a worsening from predose to postdose is observed on an ECG, repeat the ECG at the discretion of the Investigator, in addition to obtaining an ECG at the postdose time points required by the protocol. The Investigator will assess any worsening from predose to postdose in the ECG for clinical relevance (whether it meets the definition of an adverse event). Record all changes determined to meet the definition of an adverse event in the Adverse Event section of the Case Report Form.

9.5 Continuous ECGs

If a worsening is observed during the continuous ECG monitoring, the Investigator will assess the worsening for clinical relevance (whether it meets the definition of an adverse event). Record all changes determined to meet the definition of an adverse event in the Adverse Event section of the CRF.

9.6 Physical Examinations

If a worsening from predose to postdose is observed in a physical examination, repeat the physical examination at the discretion of the Investigator, in addition to obtaining a physical examination at the postdose time points required by the protocol. Document any change from predose to postdose in the Physical Examination section of the Case Report Form. The Investigator will evaluate any worsening at the postdose physical examination for their clinical relevance and to determine whether they meet the definition of an adverse event. Record all changes determined to meet the definition of an adverse event in the Adverse Event section of the Case Report Form. Record specific signs, symptoms, and/or laboratory information supporting these changes.

9.7 Vital Signs

If a worsening from predose to postdose is observed in vital signs, repeat the vital sign measurement at the discretion of the Investigator, in addition to obtaining vital sign measurements at the postdose time points required by the protocol. The Investigator will evaluate any worsening in vital signs for its clinical relevance as to whether it meets the definition of an adverse event. Record all changes determined to meet the definition of an adverse event in the Adverse Event section of the Case Report Form.

9.8 Pulse Oximetry

If a worsening is observed during the continuous pulse oximetry monitoring, the Investigator will assess the worsening for clinical relevance (whether it meets the definition of an adverse event). Record all changes determined to meet the definition of an adverse event in the Adverse Event section of the CRF.

10 Statistical Methods

Summary statistics (mean, median, standard deviation, minimum, and maximum) will be provided for continuous variables, and the number and percentage of each category will be provided for categorical data. Unless otherwise specified, the statistical tests will be 2-sided at 0.05 level of significance.

Any changes in the original statistical methodology will be documented in the statistical analysis plan (SAP).

All statistical analyses will be performed using SAS® software.

10.1 Subject Disposition and Demographic and Baseline Characteristics

Summary tables will be provided for the number of subjects who have been enrolled, dosed and completed according to the protocol. The number of subjects who prematurely discontinued the study and the reasons for their discontinuation will be summarized. Summary statistics will be presented for demographic and baseline characteristics, including age, sex, race, height, weight, BMI, and other relevant study entry criteria.

10.2 Analysis Population

Safety Analysis Population – all subjects who receive LUMASON will be included in the safety analysis population.

Efficacy Analysis Population – all subjects who receive LUMASON, and have data available at peak stress for both UE-DSE and CE-DSE and a definitive diagnosis (Positive, Negative) for CAD from truth standard (coronary angiography or 6 months follow-up data) will be included in the modified Intent-to-Diagnose (ITD) population.

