6.3 Blinding and Randomization

This is an open-label, nonrandomized study.

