8.5.3 Stress Echocardiography

Immediately after the administration of dobutamine, with or without the addition of atropine, a stress UE-DSE echocardiogram will be acquired at peak stress using harmonic imaging with the standard apical 4-, 2-, and 3-chamber views. Following the stress UE-DSE echocardiogram, a stress CE-DSE echocardiogram will be performed with administration of a single 2 mL bolus injection of LUMASON. A recording of 2D transthoracic harmonic echocardiography imaging will be performed from 30 seconds prior to injection of LUMASON and continue until all images are acquired. For both US-DSE and CE-DSE images, the apical 4-chamber view will be acquired first followed by the apical 2- and 3-chamber views.

Figure 1: Imaging Procedures

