8.6.3 Efficacy Measurements

If the subject does not complete the echocardiography examinations (rest, stress or any views are missing) the subject will not be included in the efficacy evaluation for on- or off-site.

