10.6.1.2 Evaluation of CAD

The overall diagnostic echocardiographic conclusion will be classified by the off-site readers as Normal, Abnormal or Unevaluable for unenhanced (UEUS and UE-DSE) and LUMASON-enhanced (CEUS and CE-DSE) echocardiography respectively.

The diagnostic performance of echocardiography (UE-DSE and CE-DSE) will be derived based on the diagnosis from stress echocardiography and diagnosis from truth standard (see Table E).

Table E: Cross Tabulation of Diagnosis: Truth Standard vs. Stress Echocardiography

Truth Standard (TS)	Stress Echocardiography		
	Normal	Unevaluable*	Abnormal
Negative	TN	FP	FP
Positive	FN	FN	TP

TN = true negative; TP = true positive; FN = false negative; FP = false positive

*Unevaluable is defined as: inadequate visualization of segments comprising all coronary artery territories due to motion artifacts, lateral wall drop out, swirling or attenuation artifacts.

The null hypothesis is that there is no difference in sensitivity/specificity between CE-DSE and UE-DSE at peak stress; the alternative hypothesis is that CE-DSE is superior to UE-DSE in terms of higher sensitivity/specificity:

$$H_0: \text{Diag}_{\text{CE}} - \text{Diag}_{\text{UE}} = 0,$$

$$H_a: \text{Diag}_{\text{CE}} - \text{Diag}_{\text{UE}} > 0;$$

where Diag_{CE} and Diag_{UE} denote sensitivity/specificity for CE-DSE and UE-DSE at peak stress respectively.

The sensitivity and the specificity along with their 95% confidence intervals (CIs) will be calculated, and the difference in sensitivity/specificity will be tested using McNemar's Chi-square 2-sided test.

In addition, inter-reader agreement for the detection/exclusion of CAD for CE-DSE and UE-DSE will be evaluated by kappa statistic.

10.6.2 Co-Primary Efficacy Endpoint – Critical Shift of Subjects with Suboptimal Images to Adequate Images

The co-primary endpoint: The proportion of subjects with suboptimal images (≥ 2 adjacent segments with inadequate LV EBD in any of the 3 apical views) at UE-DSE converted to adequate images (reduction of suboptimal adjacent segments to obtain adequate images) at CE-DSE will be estimated along with the 95% CIs.

Additionally, the following supportive analyses will be performed:

- proportion of subjects with optimal images at UE-DSE to suboptimal (≥ 2 adjacent segments with inadequate LV EBD in any of the 3 apical views) at CE-DSE in terms of LV EBD visualization will be estimated along with the 95% CIs.

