10.7 Sample Size

Software nQuery Advisor 7.0 is used for sample size determination in this study.

As suggested by FDA during the type C meeting on 13Aug2014, and as also reinforced and documented in the official meeting minutes issued by FDA on 24Sep2014, this study needs to demonstrate 1) a significant improvement in diagnostic performance endpoints, i.e., sensitivity/specificity from unenhanced stress imaging (UE-DSE) to contrast-enhanced stress

imaging (CE-DSE) in term of detection and exclusion of CAD, and 2) lower the CI of CE-DSE sensitivity and specificity greater than 50% (a rate greater than chance).

For significant improvement in diagnostic performance endpoints, the null hypothesis is that there is no difference in sensitivity/specificity between CE-DSE and UE-DSE at peak stress; the alternative hypothesis is that CE-DSE is superior to UE-DSE in terms of higher sensitivity/specificity:

$$H_0: \text{Diag}_{\text{CE}} - \text{Diag}_{\text{UE}} = 0,$$

$$H_a: \text{Diag}_{\text{CE}} - \text{Diag}_{\text{UE}} > 0;$$

where Diag_{CE} and Diag_{UE} denote sensitivity/specificity for CE-DSE and UE-DSE at peak stress respectively.

With 2-sided significance level (alpha) of 5%, and the probability of a Type II error (β) of 0.20, assuming expected difference between CE-DSE and UE-DSE is 25%,¹ and the proportion of discordant pairs is 40%, 45 subjects will be needed for sensitivity/specificity respectively.

For lower CI of CE-DSE sensitivity/specificity greater than 50%, assuming sensitivity/specificity of CE-DSE = 65%, about 45 CAD positive subjects are needed to have 95% confidence that the lower limit of sensitivity >50%, and 45 CAD negative subjects are needed to have 95% confidence that lower limit of specificity >50%.

Assuming approximately 30% of subjects enrolled will be CAD positive,¹³ in order to obtain 45 CAD positive subjects, 150 subjects in total need to be enrolled. With a total of 150 subjects enrolled, this will also provide more than enough CAD negative subjects according to the above calculations. The prevalence of positive subjects will be tracked based on on-site CAD diagnosis from the truth standard and if less than 30% of subjects are CAD positive, additional subjects will need to be enrolled to obtain sufficient CAD positive subjects.

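### Subjects given stress LUMASON whose CE-DSE is absent or lacks a view leave the efficacy set, while a completed unevaluable scan counts as an error; no analysis tests how much this matters

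*Combined protocol and SAP*

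**What the plan says.** - **Efficacy set (10.2).** The modified Intent-to-Diagnose population consists of subjects who received LUMASON, "have data available at peak stress for both UE-DSE and CE-DSE and a definitive diagnosis" of CAD from the truth standard.
- **Incomplete examinations (8.6.3).** This section sets an exclusion that covers both the on-site and the off-site efficacy assessment: "If the subject does not complete the echocardiography examinations (rest, stress or any views are missing) the subject will not be included".
- **Unevaluable scans (10.6.1.2, Table E).** An Unevaluable result is FP when the truth standard is negative and FN when it is positive, for either technique. "Unevaluable is defined as: inadequate visualization of segments comprising all coronary artery territories due to motion artifacts". The list of causes also names swirling, attenuation and lateral wall drop-out.
- **Order of scans (8.5.3).** "Following the stress UE-DSE echocardiogram, a stress CE-DSE echocardiogram will be performed with administration of a single 2 mL bolus injection of LUMASON". The apical 4-chamber view is acquired first, then the 2- and 3-chamber views. Section 6.3 adds: "This is an open-label, nonrandomized study".
- **Success (10.6.4).** CE-DSE must be superior for at least 2 of 3 readers. For the same readers the lower 95% limit for sensitivity/specificity must be at least 50%. For critical shift the lower limit must be above 35%.
- **Missing CE-DSE.** Section 10 has no imputation rule or sensitivity analysis for it. Section 10.8 leaves data handling to the SAP. The 15% dropout in 10.7 is not split by cause.

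**The concern.** Table E follows an intention-to-diagnose principle: a scan that gives no answer counts against the technique. The population rules stop short of that principle for one group. Take a subject who has UE-DSE images and the stress LUMASON injection, but whose CE-DSE is then not acquired or lacks a view. That subject is removed. Had poor images been recorded in all views, the same subject would have counted as a CE-DSE error.

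Because the order is fixed, a stop after UE-DSE costs CE-DSE and cannot cost UE-DSE. Within this group, entry to the analysis depends on the investigational scan having been completed.

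Such stops are foreseeable. Section 8.5.2 lists arrhythmia, hypotension and intolerable symptoms among the peak-stress endpoints, and section 5.4.3 allows discontinuation for an adverse event, without replacement. At stake are the sensitivity and specificity comparisons, the 50% floor and the critical-shift proportion.

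**Working it through.** **1. The plan's own sample size.** Inputs from 10.7: two-sided alpha 5%, power 80%, difference d = 0.25, discordant proportion ψ = 0.40. With Miettinen's approximation for McNemar's test,

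n = [1.960ψ + 0.8416√(ψ² − d²(3+ψ)/4)]² / (ψd²) = [0.784 + 0.8416 × √0.106875]² / 0.025 = 44.87, so 45.

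This reproduces the stated 45 per truth group. Enumerating the uncorrected McNemar test at n = 45 gives power 80.4%. The planned arithmetic is not at fault.

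**2. The 50% floor.** Inputs: CE-DSE 65% and n = 45 (10.7). The plan names no interval method, so Wald is assumed.

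0.65 − 1.96√(0.65 × 0.35/45) = 0.511.

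Let f be the share of the set made up of broken-off CE-DSE scored as errors. CE-DSE sensitivity becomes 0.65(1 − f), with n held at 45.

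| f (assumed) | CE-DSE | Wald lower limit |
|---|---|---|
| 0 | 65.0% | 51.1% |
| 1.6% | 64.0% | 49.9% |
| 2% | 63.7% | 49.7% |
| 5% | 61.8% | 47.6% |

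This result does not depend on whether UE-DSE was right in those subjects.

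In whole subjects, starting from 30/45 (Wald 52.9%), adding broken-off scans gives 30/47 = 50.1% and 30/48 = 48.8%. With Wilson limits, 30/46 gives 50.8% and 30/47 gives 49.5%. So the floor fails at the third added subject by Wald and at the second by Wilson.

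**3. Superiority.** Illustration near the 10.7 assumptions: 45 CAD-positive subjects, CE-DSE 30/45, UE-DSE 18/45 (40%), discordant 15 vs 3. McNemar without continuity correction: χ² = (b − c)²/(b + c).

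Add three subjects whose CE-DSE is scored as an error. Only those with a correct UE-DSE change the discordant counts.

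| UE-DSE correct among the 3 | Discordant | χ² | p |
|---|---|---|---|
| 0 | 15 vs 3 | 144/18 = 8.00 | 0.005 |
| 1 | 15 vs 4 | 121/19 = 6.37 | 0.012 |
| 2 | 15 vs 5 | 100/20 = 5.00 | 0.025 |
| 3 | 15 vs 6 | 81/21 = 3.86 | 0.0495 |

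If UE-DSE is correct 40% of the time, all three are correct with probability 0.4³ = 6.4%. Superiority is lost only with four added and all four correct on UE-DSE (15 vs 7, χ² = 64/22 = 2.91, p = 0.088).

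**4. Power and false-positive rate, under assumption.** Take f = 5% with UE-DSE correct in 40% of these subjects. The 10.7 inputs imply 32.5% correct on CE-DSE only and 7.5% correct on UE-DSE only. These become 0.95 × 0.325 = 30.9% and 0.95 × 0.075 + 0.05 × 0.40 = 9.1%. The difference is 21.8 points, and enumerated power at n = 45 falls from 80.4% to 67.0%.

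Conversely, suppose the true difference in all stress-dosed subjects were zero. Excluding 5% of them would leave an apparent gain of 0.05u/0.95 in the retained set, where u is the UE-DSE correct rate. For u = 40% to 65% this is 2.1 to 3.4 points. The chance of a significant result favouring CE-DSE would rise from 2.6% to 4.2–5.6%.

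**5. Critical shift.** With 45% and n = 150 (10.7), the lower limit is 0.45 − 1.96√(0.45 × 0.55/150) = 37.0%, as planned. Scoring 5% as not converted gives 0.45 × 0.95 = 42.75% and a lower limit of 34.8%, against the 35% bar. At 2% it is 36.2%.

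**The case against.** Several points on the other side stand.

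- **A reader might infer that the exclusions remove mainly CE-DSE failures.** The documents do not support this. They give no rate or cause, and the same rules drop subjects with no stress examination, an incomplete rest scan, an incomplete UE-DSE or no definitive truth diagnosis. None of those is a CE-DSE failure.
- **A reader might infer that the bias always favours LUMASON.** That is also too strong. The missing-view rule applies to UE-DSE too, and dropping an incomplete UE-DSE removes a UE-DSE failure. If UE-DSE was also wrong, the pair is concordant and McNemar does not change. A partial CE-DSE might already have shown an abnormality in a CAD-positive subject.
- **Table E is even-handed.** It scores both techniques, and its artifact list includes swirling and attenuation. A poor but recorded contrast view is therefore read and counted.
- **A stop is not always a contrast failure.** It may reflect dobutamine intolerance or logistics. Scoring it as a CE-DSE error in the primary analysis could bias the other way, and paired complete data are a usual basis for McNemar's test.
- **The floor is fragile anyway.** 51.1% against 50% is a thin margin whatever the population rule.
- **Section 10.2 alone is ambiguous.** Available data could include a partial CE-DSE. The explicit exclusion comes from 8.6.3.

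Summarising reasons for discontinuation (10.1) and deferring data handling to the SAP (10.8) do not answer the point. Neither changes an efficacy estimate, and the document contains no rule for a missing CE-DSE.

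**Conclusion.** The point holds in a limited form. For subjects who have UE-DSE images and received stress LUMASON, but whose CE-DSE is absent or lacks a view, 10.2 and 8.6.3 together create a one-sided, potentially informative exclusion that is at odds with Table E. It can raise CE-DSE sensitivity, specificity and critical shift.

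Its actual size cannot be computed, because no broken-off rate is given; every f above is an assumption. At the planned values, about 1.6% of the set scored as CE-DSE errors is enough to cross the 50% floor by Wald. Superiority is sturdier. With three added subjects p is 0.012 if one UE-DSE was correct and 0.0495 if all three were, so the documents do not support a reading that superiority would be lost. Nor do they require that the primary set be replaced. This is a cheap improvement.

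**What to change.** 1. Reconcile 10.2 with 8.6.3, so that one rule states whether a partial CE-DSE counts as available data.
2. Prespecify an analysis of every subject who received stress LUMASON and has a definitive truth diagnosis. Score an absent or incomplete CE-DSE as Unevaluable in Table E and as not converted for critical shift. Apply the same Unevaluable rule to an incomplete UE-DSE. State how an incomplete rest scan is handled, since this set would include it.
3. Make this at least a sensitivity analysis that must be reported beside the primary result, for each reader.
4. Report exclusions from the efficacy set by cause and by scan (rest, UE-DSE, CE-DSE, truth standard).

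The cost is protocol and SAP wording, with no new data. CE-DSE estimates in that analysis may be slightly lower, and some stops due to dobutamine or logistics will be charged to CE-DSE; the breakdown by cause lets a reader judge how many. If the sponsor made this the primary analysis, the sample size would need review: at an assumed 5% with UE-DSE 40% correct, Miettinen's formula gives 62 rather than 45 per truth group (54 to 72 for UE-DSE 20% to 65% correct).

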10.6.3 Secondary Efficacy Endpoints

For the secondary efficacy endpoint of change in total LV EBD scores at peak stress from UE-DSE to CE-DSE, the total LV EBD score is calculated as the sum of the individual scores (0, 1, or 2) assigned to each of the 17 ventricle segments with a range from 0 to 34.

For each blinded reader assessment, paired t-test will be used to compare total LV EBD score between the CE-DSE and UE-DSE. Summary statistics will be provided for the total LV EBD score from UE-DSE and CE-DSE. The change in total LV EBD score from UE-DSE to CE-DSE will be summarized along with the 95% CIs and tested by paired t-test. The cross tabulated (for UE-DSE vs. CE-DSE) distribution of the individual scores (0, 1, or 2) assigned to each of the 17 ventricle segments will be presented.

Inter-reader agreement among 3 off-site readers on the EBD score for each segment from UE-DSE and CE-DSE will be evaluated by kappa statistic.

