10.6.4 Success Criteria

The study will be considered a success if:

- for the primary efficacy endpoint of sensitivity/specificity, CE-DSE is superior to UE-DSE for at least 2 out of the 3 blinded readers and for the same 2 readers a lower limit of 2-sided 95% CI for sensitivity/specificity is $\geq 50\%$ (a rate considered greater than chance);
- for co-primary efficacy endpoint of proportion of subjects with critical shift of suboptimal images at UE-DSE to adequate images at CE-DSE, for at least 2 out of the 3 blinded readers lower limit of 2-sided 95% CI is above 35%.

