For the co-primary endpoint of critical shift from suboptimal at UE-DSE images to adequate images at CE-DSE, sample size assumptions are based on the results from the previous pivotal phase III Bracco-sponsored study (██████████).²² This study had 44.8%-46.0% of the subjects converted from suboptimal at UEUS to adequate at LUMASON-enhanced echocardiography (CEUS) at rest. When the sample size is 150, a 2-sided 95% CI for a single proportion using the large sample normal approximation will extend 8% from the observed proportion for an expected proportion of 45% subjects with critical shift from suboptimal at UE-DSE images to adequate images at CE-DSE. This can be translated as lower limit of 95% CI >35% for the observed proportion of subjects with critical shift.

Considering approximately 15% of subjects enrolled are anticipated to dropout, approximately 175 subjects will need to be enrolled.

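### The single efficacy population requires a CAD truth diagnosis, so the image-only endpoints (critical shift and total EBD score) drop imaged subjects with neither a determinate angiogram nor usable 6-month follow-up

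*Combined protocol and SAP*

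**What the plan says.** Section 10.2 defines two populations. For safety, "all subjects who receive LUMASON will be included in the safety analysis population". For efficacy there is one set, the modified intent-to-diagnose population: dosed subjects who "have data available at peak stress for both UE-DSE and CE-DSE and a definitive diagnosis (Positive, Negative) for CAD from truth standard".

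The critical-shift co-primary in 10.6.2 is "The proportion of subjects with suboptimal images (≥ 2 adjacent segments with inadequate LV EBD in any of the 3 apical views) at UE-DSE" that is "converted to adequate images (reduction of suboptimal adjacent segments to obtain adequate images) at CE-DSE will be estimated along with the 95% CIs". For the secondary endpoint in 10.6.3, "the total LV EBD score is calculated as the sum of the individual scores (0, 1, or 2) assigned to each of the 17 ventricle", that is, over all segments of the model; it is compared between UE-DSE and CE-DSE. Neither definition refers to angiography or follow-up, and neither section names its own population.

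The success rule for critical shift in 10.6.4 is that "for at least 2 out of the 3 blinded readers lower limit of 2-sided 95% CI is above 35" percent. Section 10.7 bases this on 150 subjects, for whom the interval "will extend 8% from the observed proportion for an expected proportion of 45% subjects with critical shift". It then applies one overall loss rate: "Considering approximately 15% of subjects enrolled are anticipated to dropout, approximately 175 subjects will need to be enrolled".

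On the truth standard, 8.6.4 sends subjects with no angiogram, or an indeterminate one, to 6-month follow-up. Section 10.6.1.1 classes those with a listed cardiac event as Positive and the rest as Negative. Separately, 8.6.3 removes subjects with incomplete echocardiography from efficacy.

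**The concern.** A truth diagnosis is an input to sensitivity and specificity but not to endocardial border visualization. Because 10.2 offers only one efficacy set, the truth condition carries over to endpoints that have no use for it. A subject with complete UE-DSE and CE-DSE images at peak stress, but no determinate angiogram and no usable follow-up, has full data for critical shift and EBD score and still drops out of both.

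Two things are at stake. The first is precision on a co-primary whose planned lower limit is about 2 points above its 35% bar. The second is selection. Truth status is settled after imaging, up to 6 months later. The study is open-label (6.3), and the on-site investigator makes a CAD diagnosis from both sets of echo images (8.6.1). Whether a subject ends up with a truth diagnosis might therefore be related to what the images showed.

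**Working it through.** **Inputs.** From 10.7: expected shift proportion 45%, n = 150, about 15% loss, about 175 enrolled, 30% prevalence, 45 CAD-positive subjects. From 10.6.4: lower 95% limit above 35%. The documents do not say what share of the 15% is missing truth data, so the full range is shown as an assumption.

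**1. The plan's own figures.**
- Total before dropout: 45 / 0.30 = 150.
- Half-width: 1.96 × √(0.45 × 0.55 / 150) = 7.96 points, so the lower limit is 45 − 7.96 = 37.0%. This matches the stated 8% and the stated limit above 35%.
- Enrolment: 150 / 0.85 = 176.5, or 177 rounded up; 150 × 1.15 = 172.5, or 173. The stated figure of about 175 lies between them.

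No stated figure is wrong.

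**2. Who is dropped.** Reading 8.6.4, 10.6.1.1 and 10.2 together:
- determinate angiogram: classed, kept;
- no angiogram or an indeterminate one, follow-up completed, event: Positive, kept;
- the same, follow-up completed, no event: Negative, kept;
- neither a determinate angiogram nor usable follow-up: no definitive diagnosis, dropped.

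Only the last group is affected.

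**3. Effect of lifting the condition for the image endpoints.** With 175 enrolled, the current set is 175 × 0.85 = 148.75, about 149, a loss of 26. Half-width = 1.96 × √(0.2475 / n).

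| Assumed share of the 26 losses due to missing truth | n | Half-width (points) | Lower limit at observed 45% |
|---|---|---|---|
| 0% | 149 | 7.99 | 37.0% |
| 25% | 155 | 7.83 | 37.2% |
| 50% | 162 | 7.66 | 37.3% |
| 75% | 169 | 7.50 | 37.5% |
| 100% | 175 | 7.37 | 37.6% |

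The largest possible gain is 7.99 − 7.37 = 0.62 points on the lower limit. At an observed 45% the rule is met for any n of 96 or more, since (1.96 / 0.10)² × 0.2475 = 95.1. It is therefore met with or without the change.

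**4. Selection, as an illustration only.** If a fraction f of imaged subjects lacks a truth diagnosis and their shift rate differs by d points from that of the retained subjects, the estimate moves by f × d. With assumed values, f = 5% and d = 10 gives 0.5 points; f = 10% and d = 20 gives 2 points. The second would equal the planned margin of 37.0 − 35 = 2 points. The documents support no particular f or d, and no direction.

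**The case against.** **The affected group may be small or empty.** Entry requires scheduled angiography (5.4.1), and follow-up combines record review with a phone call (8.6.4.2). Read literally, the residual clause in 10.6.1.1 could class even lost subjects as Negative, leaving nobody to exclude. This stands as a limit on size. It does not remove the point: the requirement of a definitive diagnosis in 10.2 would then do almost nothing, and the two sections need to be made consistent in any case.

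**Much of the 15% may be imaging loss.** Incomplete examinations are excluded under 8.6.3, and the proposed set would not recover subjects without peak-stress images. This stands, and it makes the 100% row in the table a ceiling rather than an expectation.

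**A common set for both co-primaries is defensible.** It keeps them on the same subjects. But 10.6.4 judges each co-primary by its own rule, so sharing a set gives the image endpoints no benefit.

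**The application is inferred.** Sections 10.6.2 and 10.6.3 name no population, and Section 10 refers to a SAP for changes and data handling. The supplied documents contain no other efficacy population, so the inference is reasonable but not certain.

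**Stronger readings that a reader might infer, and that the documents do not support:**
- *Every subject without angiography is lost.* Section 10.6.1.1 classes and keeps those who complete follow-up.
- *The restriction costs several points of power.* The exact per-reader chance of a Wald lower limit above 35% at a true 45% is 0.688 at n = 150 and 0.740 at n = 175, which looks like a clear gain. But it is 0.720 at n = 149 and 0.704 at n = 162. At these sample sizes the differences largely reflect binomial discreteness. The half-width is the steadier measure.
- *The critical-shift estimate is biased.* Section 5.2 says that not everyone will have angiography, but does not link this to the echo result.

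**Conclusion.** The point holds as a structural defect of modest size. Applied as written, 10.2 removes imaged subjects from a co-primary and the secondary efficacy endpoint on a condition that neither endpoint uses. The group is limited to those with neither a determinate angiogram nor usable 6-month follow-up, and the plan gives no count.

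Under the plan's 15% loss, the precision cost is at most about 0.6 points of half-width, and less if part of the loss is imaging failure. Selection bias is possible but not shown.

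This rests on two assumptions: that the single efficacy set applies to the image endpoints by default, and that the denominator for critical shift is all evaluable subjects, as 10.7 assumes with n = 150. If the denominator is only subjects suboptimal at UE-DSE, every n above is smaller; that is a separate question.

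**What to change.** In 10.2, define two efficacy sets:

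- **Image-evaluable set:** received LUMASON and has peak-stress data for both UE-DSE and CE-DSE, regardless of truth standard. Use it for critical shift and total EBD score.
- **Diagnostic set:** the same, plus a definitive Positive or Negative truth diagnosis. Use it for sensitivity and specificity only.

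Name the applicable set in 10.6.1, 10.6.2 and 10.6.3. State in 10.6.1.1 whether a subject lost before 6 months without a determinate angiogram is Negative or has no definitive diagnosis. Report the number of imaged subjects outside the diagnostic set. The completeness rule in 8.6.3 is unaffected.

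The cost is a sentence or two and one population flag. No new data are needed and the sensitivity and specificity analysis does not change. The small downside is that the two co-primaries would be reported on slightly different sets. Make the change before reader results are linked to truth diagnoses, so that the choice of population cannot appear data-driven.
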